**Statistical Analyses**

The primary efficacy endpoint is the absolute change in ppFEV₁ from baseline at Week 4. The primary null hypothesis to be tested is that the mean absolute change in ppFEV₁ from baseline at Week 4 is the same for the TC and TEZ/IVA treatment groups. The null hypothesis will be tested at a 2-sided significance level of 0.05.

Assuming a within-group SD of 7 percentage points and a 5% dropout rate at Week 4, a sample size of 50 subjects in each treatment group for a total of 100 subjects will have approximately 93% power to detect a difference of 5.0 percentage points for the mean absolute change in ppFEV₁ from baseline at Week 4 between the 2 treatment groups, based on a 2-sided 2-sample *t*-test at a significance level of 0.05.

The primary analysis will be based on a mixed-effects model for repeated measures (MMRM). The model will include the absolute change from baseline in ppFEV₁ at Day 15 and Week 4 as the dependent variable; treatment group, visit, and treatment-by-visit as fixed effects; with continuous baseline ppFEV₁ and age at screening (<18 versus ≥18 years of age) as covariates; and an unstructured covariance structure for the within-subject errors.

The primary result obtained from the model will be the estimated treatment difference at Week 4. The adjusted mean with a 2-sided 95% CI and a 2-sided *P* value will be provided.

The safety endpoints include AEs, clinical laboratory values, ECGs, vital signs, and pulse oximetry through the Safety Follow-up Visit. The safety analysis will be descriptive only.

IDMC Reviews An independent data monitoring committee (IDMC) will conduct safety review of study data as outlined in the IDMC charter.

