^d Any female subject who does not meet the criteria for non-childbearing potential is considered to be of childbearing potential and must have a serum pregnancy test. A definition of non-childbearing potential is provided in [Section 11.7.7.1](#).

^e Weight and height will be measured with shoes off.

^f Ophthalmologic examinations will be conducted only for subjects who are <18 years of age on the date of informed consent. For subjects with documentation of bilateral lens removal, ophthalmologic examinations are not required. The ophthalmologic examination does not need to be conducted if there is documentation of an examination meeting the protocol requirements that was conducted within 3 months before the date of informed consent ([Section 11.7.6](#)). The ophthalmologic examination will be conducted by a licensed ophthalmologist or optometrist.

^g Vital signs and pulse oximetry will be collected after the subject has been at rest for at least 5 minutes.

^h A standard 12-lead ECG will be performed after the subject has been at rest for at least 5 minutes.

ⁱ Spirometry may be performed pre- or post-bronchodilator ([Section 11.6.1](#)).

^j Refer to [Section 9.5](#) for details.

Table 3-2 VX17-659-103: TEZ/IVA Run-in Period, Treatment Period, and Safety Follow-up Visit

Event/Assessment ^a	TEZ/IVA Run-in Period (4 Weeks)		Treatment Period (4 Weeks)			ETT Visit ^b	Safety Follow-up Visit 28 (± 7) Days After the Last Dose of Study Drug (If Applicable) ^c
	Day -28 ± 1 Day	Day -14 (Day -15 to Day -3)	Day 1 ^d	Day 15 ± 3 Days	Week 4 ± 5 Days		
Clinic visit	X	X	X	X	X	X	X
Inclusion and exclusion criteria confirmation	X						
CFQ-R ^e			X	X	X	X	X
Weight and height ^f	X		X	X	X	X	X
Physical examination ^g	Abbreviated		Complete		Complete	Complete	
Pregnancy testing ^h	Urine		Urine		Urine	Serum	Serum
Standard 12-lead ECG ⁱ	X		X	X	X	X	X

^a All assessments will be performed before dosing unless noted otherwise.

^b If the subject prematurely discontinues study drug treatment, an ETT Visit should be scheduled as soon as possible after the decision to discontinue treatment. Subjects who prematurely discontinue treatment during the Treatment Period will continue to complete all scheduled study visits for assessments following completion of the ETT Visit (Section 9.1.5.2).

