^c The Safety Follow-Up Visit is required for all subjects, unless the subject completes the Week 4 Visit and has enrolled in a separate open-label study within 28 days after the last dose of study drug (Section 9.1.4). If an ETT Visit occurs 3 weeks or later following the last dose of study drug, then the ETT Visit replaces the Safety Follow-up Visit (Section 9.1.5).

^d To enter the Treatment Period, conditions for entry (Section 9.1.3) must be satisfied.

^e The CFQ-R, [REDACTED] must be completed before any other assessments scheduled at relevant visits. Refer to Section 11.6.2 and [REDACTED]

^f Weight and height will be measured with shoes off. Following screening, height will be collected only for subjects ≤21 years of age on the date of informed consent.

^g Abbreviated and complete physical examinations are defined in Section 11.7.3. Symptom-directed physical examinations will occur at any time during the study if deemed necessary by the investigator.

^h Any female subject who does not meet the criteria for non-childbearing potential is considered to be of childbearing potential and must have pregnancy testing at the indicated time points. A definition of non-childbearing potential is provided in Section 11.7.7.1.

ⁱ All standard 12-lead ECGs will be performed after the subject has been at rest for at least 5 minutes. ECGs will be collected before dosing (as applicable).

Table 3-2 VX17-659-103: TEZ/IVA Run-in Period, Treatment Period, and Safety Follow-up Visit

Event/Assessment ^a	TEZ/IVA Run-in Period (4 Weeks)		Treatment Period (4 Weeks)			ETT Visit ^b	Safety Follow-up Visit 28 (± 7) Days After the Last Dose of Study Drug (If Applicable) ^c
	Day -28 ± 1 Day	Day -14 (Day -15 to Day -3)	Day 1 ^d	Day 15 ± 3 Days	Week 4 ± 5 Days		
Vital signs ^j	X		X	X	X	X	X
Pulse oximetry ^j	X		X	X	X	X	X
Spirometry ^k		X	X	X	X	X	X
Sweat chloride ^l		X	X	X	X	X	
Urinalysis	X		X		X	X	X
Hematology	X ^m		X ^m	X	X	X	X
Coagulation	X ^m		X ^m		X	X	X
Serum chemistry	X ^m		X ^m	X	X	X	X
PK sampling ⁿ			X		X	X	

^j Vital signs and pulse oximetry will be collected before dosing and after the subject has been at rest for at least 5 minutes.

^k Spirometry assessments must be performed before study drug dosing (see [Section 9.6.1](#)) and should be performed pre-bronchodilator ([Section 11.6.1](#)) at approximately the same time at each visit.

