12.3 Statistical Analysis

12.3.1 General Considerations

Continuous variables will be summarized using the following descriptive summary statistics: the number of subjects (n), mean, SD, median, minimum value (min), and maximum value (max). The precision of the measurement for each continuous variable will be specified in the SAP. Unless otherwise specified, min and max values will be reported with the same precision as the units of the raw data. The mean, median, and SD will be reported to 1 additional decimal place. Any values that require a transformation to standard units (metric or SI) will be converted with the appropriate precision.

Categorical variables will be summarized using counts and percentages. Percentages will be presented to 1 decimal place.

The **baseline value**, unless otherwise specified, will be defined as the most recent non-missing measurement (scheduled or unscheduled) collected before the first dose of study drug in the Treatment Period (i.e., the Day 1 Visit). For ECG, baseline will be defined as the most recent pretreatment measurement (or the average of triplicate measurements, if the most recent pretreatment measurement is obtained in triplicate) before the first dose of study drug in the Treatment Period (i.e., the Day 1 Visit).

Absolute change from baseline will be calculated as post-baseline value – baseline value.

The **Treatment-emergent (TE) Period for the Run-in Period** will be from the first dose of study drug in the Run-in Period to (1) the first dose of study drug in the Treatment Period for subjects who complete the Run-in Period and continue to the Treatment Period, or (2) 28 days after the last dose date of study drug in the Run-in Period for subjects who do not continue to the Treatment Period (e.g., subjects who do not meet the conditions to enter the Treatment Period).

The **TE Period for the Treatment Period** will include the time from the first dose date of study drug in the Treatment Period (TC or placebo + TEZ/IVA) to 28 days after the last dose of the study drug or to the completion of study participation date (as defined in [Section 9.1.7](#)), whichever occurs first.

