12.3.4 Safety Analysis

All safety analyses will be based on data from the TE Period for all subjects in the Safety Set.

The overall safety profile of study drug will be assessed based on the following safety and tolerability endpoints:

- Treatment-emergent adverse events (TEAEs)
- Clinical laboratory values (i.e., hematology, serum chemistry, coagulation, and urinalysis)
- ECGs
- Vital signs
- Pulse oximetry

All safety data from the TE Period will be summarized by treatment group and overall.

All safety data will be presented in individual subject data listings, including safety data from the Run-in Period.

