## 9 STATISTICAL ANALYSIS

### 9.1 General Considerations

The Schedule of Assessments is provided in Section 3 of CSP. The precision standards for reporting safety and efficacy variables are provided in an internal Biometrics document that specifies the programming rules including the precision for derived variables.

**Continuous variables** will be summarized using the following descriptive summary statistics: the number of subjects (n), mean, SD, median, minimum value (min), and maximum value (max).

**Categorical variables** will be summarized using counts and percentages. Percentages will be presented to 1 decimal place.

**Baseline value**, unless otherwise specified, is defined as the most recent non-missing measurement (scheduled or unscheduled) collected before the first dose of study drug in the Treatment Period.

**Absolute change** from baseline will be calculated as post-baseline value – baseline value.

**Relative change** from baseline will be calculated as (post-baseline value – baseline value)/baseline value.

The **Treatment-emergent (TE) Period for the Run-in Period** will be from the first dose of study drug in the Run-in Period to (1) the first dose of study drug in the Treatment Period for subjects who complete the Run-in Period and continue to the Treatment Period, or (2) 28 days after the last dose date of study drug in the Run-in Period for subjects who do not continue to the Treatment Period (e.g., subjects who do not meet the conditions to enter the Treatment Period).

The **TE Period for the Treatment Period** will include the time from the first dose date of study drug in the Treatment Period (TC or placebo + TEZ/IVA) to 28 days after the last dose of the study drug or to the completion of study participation date, whichever occurs first.

Completion of study participation for each individual subject is defined as one of the following:

- For subjects who complete the Treatment Period and enter an open-label study within 28 days of the Week 4 Visit: the Week 4 Visit
- For subjects who complete the Treatment Period and do not enter an open-label study within 28 days of the Week 4 Visit: the Safety Follow-up Visit
- For subjects who prematurely discontinue study drug treatment during the Treatment Period but do not withdraw consent (and assent, as applicable): The ETT or Safety Follow-up Visit (if required)

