- For subjects who prematurely discontinue study drug treatment during the TEZ/IVA Run-in Period but do not withdraw consent (and assent, as applicable): the ETT or Safety Follow-up Visit (if required)
- For subjects who withdraw consent or assent: date of withdrawal of consent or assent, whichever is earlier

If subjects are lost to follow-up, the date of completion of study participation will be defined as the date of the last contact.

**Unscheduled visits:** Unscheduled visit measurements will be included in analysis as follows:

- 1) In scheduled visit windows per specified visit windowing rules
- 2) In the derivation of baseline and last on-treatment measurements
- 3) In the derivation of maximum and minimum values during TE period, and maximum and minimum change from baseline values during TE period for safety analyses
- 4) In individual subject data listings as appropriate

**Visit windowing rules:** The analysis visit windows for protocol-defined visits are provided in [Appendix A](#).

**Incomplete/missing data** will not be imputed, unless specified otherwise.

**Outliers:** No formal statistical analyses will be performed to detect or remedy the presence of statistical outliers, unless specified otherwise.

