## 9.4 Safety Analysis

All safety analyses will be based on data from the TE period for the Treatment Period for all subjects in the corresponding Safety Set for the Treatment Period, unless otherwise specified. Subjects will be analyzed according to the treatment they actually received in the Treatment Period. For subjects receiving study drug from more than one treatment group, the treatment group allocation will be the higher treatment group (VX-659/TEZ/IVA > TEZ/IVA).

The overall safety profile of study drug will be assessed in terms of the following safety and tolerability endpoints:

- Treatment-emergent adverse events (TEAEs)
- Clinical laboratory values
- ECGs
- Vital signs
- Pulse oximetry

Only descriptive analysis of safety will be performed and no statistical testing will be performed. The safety data during the Run-in Period will only be presented in listings, unless otherwise specified.

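### Should the treatment-emergent period run to day 35, so that laboratory, ECG, vital-sign and oximetry values from late but in-window Safety Follow-up Visits enter the threshold and shift tables?

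*SAP*

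**What the plan says.** **Cut-off.** Protocol 12.3.1 starts the TE period of the Treatment Period at the first dose in that period and runs it "to 28 days after the last dose of the study drug or to the completion of study participation date", taking the earlier of the two. SAP 9.1 repeats the rule: "to 28 days after the last dose of the study drug or to the completion of study participation date, whichever occurs first". For completers who do not roll over, participation ends at the Safety Follow-up Visit (protocol 9.1.7, SAP 9.1).

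**Visit window.** Table 3-2 heads the column "Safety Follow-up Visit 28 (± 7) Days After the Last Dose of Study Drug". Hematology, chemistry, coagulation, ECG, vital signs and oximetry are all scheduled there. Footnote c adds "The Safety Follow-Up Visit is required for all subjects, unless the subject completes the Week 4 Visit" and enrols in an open-label study within 28 days of the last dose.

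**Scope of the safety outputs.** Protocol 12.3.4: "All safety analyses will be based on data from the TE Period for all subjects in the Safety Set". SAP 9.4: "All safety analyses will be based on data from the TE period for the Treatment Period", with an allowance for exceptions specified elsewhere. SAP 9.4.2 to 9.4.5 tie the threshold tables, the oximetry shift table and the liver-test plots to that period. Item 3 of the unscheduled-visit rule in SAP 9.1 does the same: "In the derivation of maximum and minimum values during TE period".

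**Synopsis.** "The safety endpoints include AEs, clinical laboratory values, ECGs, vital signs, and pulse oximetry through the Safety Follow-up Visit".

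**Visit labels.** SAP Table 12-1 assigns laboratory, ECG and vital-sign data to Safety Follow-up by nominal visit, with no day limit. Its note 4 maps an Early Termination of Treatment (ETT) visit there only when no nominal follow-up visit exists and the study day is above 43.

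**The concern.** A subject seen on day 28 after the last dose and another seen on day 29 are equally compliant. If both have the same raised ALT, only the first enters the threshold table and the liver-test plot. The booking date then decides whether a scheduled safety value is tabulated, while the synopsis reads as if the safety endpoints extend to the follow-up visit itself.

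Two further points look untidy.

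- The by-visit laboratory, ECG and vital-sign summaries are described as treatment-emergent, but Table 12-1 takes the nominal follow-up visit whatever its day. The Safety Follow-up row could therefore be built in two ways. Table 12-1 also has no oximetry row.
- Protocol 9.1.5 lets an ETT visit three weeks or more after the last dose stand in for Safety Follow-up, whereas note 4 uses study day 43 as its threshold.

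At stake would be the completeness of the off-drug safety tables, chiefly for liver tests.

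**Working it through.** The plan gives no figure of its own on this point, so the check is a count of days and a comparison of rules.

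**1. Window against cut-off** (days after the last dose)

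- Permitted visit days: 28 − 7 = 21 to 28 + 7 = 35, which is 35 − 21 + 1 = 15 days.
- For a visit on day d by a subject who does not roll over, participation ends on day d, so the TE period ends on day min(28, d).
- For d = 21 to 28, min(28, d) = d and the value is included: 8 days.
- For d = 29 to 35, min(28, d) = 28 and the value is excluded: 7 days.

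So 7 of the 15 permitted days fall outside. This counts calendar days; it is not a share of visits, since sites aim at day 28.

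**2. The same in study days.** The last dose is taken the evening before the Week 4 Visit, so with that visit on its target study day 29 the last dose is on study day 28. The TE period ends by 28 + 28 = 56. The window runs from 28 + 21 = 49 to 28 + 35 = 63. Study days 57 to 63 are outside, again 7 days.

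**3. Where an excluded value still appears**

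- Listings: protocol 12.3.4 puts all safety data in individual listings. The laboratory, ECG and vital-sign listings in SAP 9.4.2 to 9.4.4 cover scheduled and unscheduled visits.
- Adverse events: protocol 13.1.1.2 turns a clinically significant worsening into an adverse event. Protocol 13.1.1.3 collects events until participation ends, which here is the follow-up visit. SAP 9.4.1 defines and lists post-treatment events.
- By-visit tables: SAP 9.4 permits exceptions, and the nominal-visit rule in Table 12-1 reads naturally as one. On that reading a late laboratory, ECG or vital-sign value is still summarised under Safety Follow-up, and only thresholds, shifts and maxima are capped.

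**4. The ETT rule.** Let L be the study day of the last dose. The protocol lets ETT replace Safety Follow-up from study day L + 21; note 4 relabels it only above day 43. The two differ when L + 21 ≤ 43, that is L ≤ 22. Take L = 10 and ETT on day 35:

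- 35 − 10 = 25 days after the last dose, so under the protocol the visit replaces Safety Follow-up.
- Day 35 lies in the Week 4 analysis window, which covers days above 22 and up to 43.
- The 28-day limit falls on day 10 + 28 = 38, so the value is inside the TE period and nothing is lost from the threshold, shift or maximum outputs.

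Only the label differs. The case also needs an ETT visit at least three weeks late, although protocol 9.1.5 asks for it as soon as possible.

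**5. What an extension to day 35 would do**

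- It would depart from protocol 12.3.4, which limits safety analyses to the TE period.
- A laboratory value on days 29 to 35 could count in a threshold table while the adverse event it gave rise to stayed post-treatment.
- It would add values from more than four weeks off study drug. Table 9-2 lifts the bar on Vertex CFTR modulators after the last dose, so such values may reflect other treatment.
- A 35-day limit applied to note 4 would remove nominal follow-up visits after day 35 that note 4 now keeps. Dependence on the booking day would move by a week, not disappear.

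**The case for a change.** The strongest case for a change is that the tables and plots, not the listings, are what readers use to judge liver and ECG safety, and a compliant visit should not drop out of them because of its date. Off-drug values up to day 28 are already included, so one more week breaks no principle. The synopsis suggests that the follow-up visit was meant to count, and one sentence in the SAP would be enough.

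The arithmetic behind this stands: values on days 29 to 35 are left out of those outputs. The inference of an error does not. The synopsis names the data the safety endpoints draw on and says the analysis is descriptive; it does not promise threshold tables to that visit. The detailed sections of both documents limit the analyses to the TE period. A visit tolerance of 7 days either way is operational and does not oblige the analysis period to match it. Any fixed cut-off treats neighbouring days differently.

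The labelling points also stand as gaps in detail. Protocol 12.3.4 does not carry the allowance for exceptions that SAP 9.4 has, so the SAP could have said outright that Table 12-1 governs the by-visit tables. Analysts can settle this sensibly by using the nominal visit. They can handle oximetry like the vital signs, which Table 3-2 schedules at the same visits.

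**Conclusion.** No change is needed. The 28-day cut-off is a consistent, pre-specified choice, and moving it for four data types alone exchanges one imperfection for others that a sponsor could reasonably decline.

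The effect is small. It covers 7 of 15 permitted days, none of them the target day, and only subjects who attend a Safety Follow-up Visit; those who complete Week 4 and roll over within 28 days need none. No hypothesis test, adverse-event count or medication category is affected. Because sites and subjects are blinded, there is no reason to expect late booking to differ by arm.

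This rests on two assumptions: that most visits are booked near day 28, and that the listings and adverse-event reporting work as described. The documents do not give the number of subjects seen on days 29 to 35. The by-visit row, the missing oximetry row and the ETT label are details that analysts can settle without altering any conclusion.

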## **9.2 Background Characteristics**

### **9.2.1 Subject Disposition**

A disposition table will be provided for the Run-in Period with the following categories:

- All Subjects Set
- Safety Set for the Run-in Period

The number and percentage (based on Safety Set for the Run-in Period) of subjects in each of the following disposition categories will be summarized:

- Prematurely discontinued treatment before randomization and the reason for treatment discontinuation
- Prematurely discontinued study before randomization and the reason for study discontinuation

A separate disposition table will be provided for the Treatment Period with the following categories:

- Full Analysis Set
- Safety Set for the Treatment Period
- Randomized
- Randomized but not dosed in the Treatment Period
- Randomized or dosed in the Treatment Period

The number and percentage (based on FAS) of subjects in each of the following disposition categories will be summarized by treatment group and overall:

- Completed study drug treatment
- Prematurely discontinued treatment and the reason for discontinuation (i.e., discontinued all study drugs)
- Completed study
- Prematurely discontinued the study and the reason for discontinuation
- Rollover to the open-label study

A listing will be provided for subjects who discontinued treatment (including both the Run-in Period and Treatment Period) or who discontinued study with reasons for discontinuation.

### **9.2.2 Demographics and Baseline Characteristics**

Demographics and baseline characteristics will be summarized based on the FAS, and presented by treatment group and overall, as applicable.

Demographic data will include the following:

- Age at baseline (in years)

- Sex (female and male)
- Ethnicity (Hispanic or Latino, not Hispanic or Latino, and not collected per local regulations)
- Race (White, Black or African American, Asian, American Indian or Alaska Native, Native Hawaiian or Other Pacific Islander, and not collected per local regulations)
- Geographic region (North America, Europe [including Israel and Australia])

Baseline characteristics will include the following:

- Weight (kg)
- Height (cm)
- BMI (kg/m^2)

Stratification categories will include the following:

- Age at Screening Visit (<18, ≥18 years)
- ppFEV1 at Day -14 (<70, ≥70)

Disease characteristics will include the following:

- ppFEV1 at baseline (<40, ≥ 40 to <70, ≥70 to ≤90, and >90)
- ppFEV1 at baseline (continuous)
- Sweat chloride at baseline (continuous)
- CFQ-R respiratory domain score at baseline (continuous)
- Prior use of dornase alfa before first dose of study drug in the Treatment Period (Yes, No)
- Prior use of azithromycin before first dose of study drug in the Treatment Period (Yes, No)
- Prior use of inhaled antibiotic before first dose of study drug in the Treatment Period (Yes, No)
- Prior use of bronchodilator before first dose of study drug in the Treatment Period (Yes, No)
- Prior use of inhaled bronchodilator before first dose of study drug in the Treatment Period (Yes, No)
- Prior use of inhaled hypertonic saline before first dose of study drug in the Treatment Period (Yes, No)
- Prior use of inhaled corticosteroids before first dose of study drug in the Treatment Period (Yes, No)
- Infection with *Pseudomonas aeruginosa* within 2 years prior to screening (Positive, Negative)

In addition, data listings will also be provided for:

- Informed consent;
- Inclusion/Exclusion criteria violation for subjects with any such violations.

